To examine the effects of price (and the interactive effects of prices and peers) on perceptions and technology adoption, both S1 and S2 Groups will be randomly subdivided into multiple price treatment groups. The price randomization will be done at the cluster level – i.e., all households in a cluster will be offered stoves at the same price. Using data from the REACCTING study and pretesting activities, we will set a range of prices for both types of stoves being offered. We will then generate a factorial design that creates different combinations of prices for the two stoves, and randomize these price levels across clusters, balancing prices across **S1** and **S2** clusters. The number of replicates for each price level will be determined to maximize the information expected to be generated from the intervention, using modeling based on parameters derived from pretesting data.

At the given price level, households will choose whether they would like to receive/purchase no stoves, one stove, or two stoves. In addition, households will be able to choose *which type(s)* of stoves they would like: the Gyapa-type (Greenway) or the Philips-type (ACE) stove.

Varying price levels is necessary to our research design and central to our ability to generate one of the key study benefits, namely, information on households' willingness to pay for clean cookstoves in this region. At the same time, we recognize that offering households stoves at different prices has the risk of being seen as creating an unequal burden or inequitable benefits for study participants. Regarding the *burden* for respondents, we emphasize that respondents will be free to choose whether or not to purchase stoves at the given price. This will be emphasized throughout the study, at enrollment and at the time when stoves are offered, and every attempt will be made to ensure that respondents do not feel undue pressure to select to buy a stove. Furthermore, price levels will be set for the two stoves based on an initial phase of focus group and pretesting. Stove prices will be set at or below the actual stove costs –

that is, households will not be asked to pay more than the stoves are actually worth. Finally, we will offer financing options to respondents to allow them to pay for their stoves over time. This may allow some households who would like to buy stoves but face credit constraints in the short term to do so, reducing the burden of paying for stoves all at once.

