Since some households will be offered stoves for free while others will be offered stoves at positive prices, the benefits will be *unequal* across participants. However, these prices will be varied *at random*, such that the benefits will not be *inequitable*: at the outset of the study, all respondents will have an equal chance of being assigned to different price levels. This study design will be clearly explained to participants at the outset, as described in the Recruitment section (VIII) and specified in the Consent Form. Randomization of clusters to different price levels will be done in a participatory and transparent manner – for example, we may conduct the randomization during a meeting involving representatives from the different clusters, allowing these individuals to draw numbers out of a hat to determine their clusters' stove price levels, and videotaping this process so that it is available to show respondents concerned about the fairness of the price assignment.

Analysis of Key Research Questions and Power Calculations

Econometric analysis of data from the experiments will estimate regression models for three key outcome variables: stove adoption, use, and perceptions of quality (pre- and post-adoption). Multiple indicators of each of these outcomes will be possible. For example, adoption measures can include binary indicators for purchase / receipt of *any* stove, as well as indicators for the number and type(s) of stoves selected. Stove use measures will come from surveys and electronic monitors, and can be specified at the stove or household level over various time periods (e.g., reported use on previous day from survey vs number of uses over a month from SUMs). Perceptions measures can include overall favorable / unfavorable ratings as well as more continuous measures from Likert-scale and/or subjective expectation responses.

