Study households will be randomly selected from the sample frame of eligible households constructed using the methods described in Part VI. Following local customs for conducting research in this area, community entry and engagement activities will be conducted in all study clusters prior to beginning research activities. The study's community entry, education, and engagement activities are designed to serve at least three key objectives. First, we understand the need to respect local customs and obtain the proper permissions to conduct our study in each area. To this end, we will hold community entry meetings and engage local chiefs and sub-chiefs to explain the objectives of our study and enlist their support in carrying out these objectives. NHRC collaborators with extensive knowledge of the local context and norms will lead this effort. In addition, while our study will deal extensively with female household members who are most closely involved in cooking activities, interviewers and other study personnel will also engage household heads to fully inform them of the study's methods and objectives.

A second objective of the community entry and engagement activities is to address any concerns participants may have and foster trust in the study's objectives and fairness. Through the community entry meetings described above, we will explain our methods as transparently as possible and communicate with leaders and participants at various levels. For example, one question that might arise is why certain clusters or households have been chosen for inclusion in the study. Through our community entry activities, we can explain that this selection was done randomly. Since women will be heavily involved in the study, we also want to ensure that these women are approached in a respectful way and that they feel comfortable raising any concerns, they may have. For this reason, we will also use the community entry meetings to identify local women groups and engage them in the community outreach processes.

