The study's experimental manipulation of stove price will also be clearly explained during the community entry and recruitment activities. For P3 Bio, we will tell participants the price of the two stoves, and then explain that households in different clusters will be offered varying discounts to purchase the stoves if they choose. We will also explain that these discounts are set randomly, and will randomize the stove discounts transparently during the community entry phase with the participation of representatives from different clusters. (For example, this may be done by allowing representatives from the different study clusters to draw numbers out of a hat to determine their clusters' price levels.) Regarding the peer effect manipulation, we will disclose to participants that we are conducting the study in different areas, and that stoves have already been distributed to some households through a prior study that was conducted in some but not all of these areas. For P3 Gas, we will explain that the LPG stove-fuel packages being offered are available in the market (and tell households the market value of the packages). The auction mechanism will be clearly explained, with an emphasis on the randomized nature of the offer prices and the importance of stating one's true willingness to pay. As long as participants report their willingness to pay accurately (i.e., do not overstate their willingness to pay), they will not be required to pay more than the amount they are willing for any of the stove packages.

Following community entry, households that have been randomly selected from each cluster will be visited by the survey interviewers. These interviewers will inform the households of their selection for inclusion in the study, describe the study purpose and procedures, and obtain informed consent from participants. Interviewers will make it clear that participation is purely voluntary and will not coerce participation in any way. No written / visual recruitment materials will be used; interviewers will approach recruits in person (following standard practices in this area). A list of replacement households from each cluster will be randomly draw along with the initial recruits; households that elect not to participate (or are not available / cannot be located) will be replaced with households from this list.

P3 Gas Supply Survey Recruitment

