For the LPG supply survey, NHRC interviewers will visit each business, ask to speak to the owner or manager, and explain the purpose of the survey. These individuals will then be read the informed consent statement, and will indicate whether they agree to participate in the survey.

IX. COMPENSATION

Small in-kind tokens of appreciation are offered to study participants as compensation. These include items such as bags of rice, bars of soap, or cell phone credits. As with all aspects of the field work, we defer to our local collaborators for guidance on appropriate, non-coercive methods of compensation for study participants.

X. CONSENT PROCESS

Informed consent will be obtained for all study participants at the outset of this study. Given that the study poses minimal risks to participants, oral consent will be obtained. The enclosed consent statement describes the purpose of the research and the research design, including the design of the experimental manipulations of price and peer effects, and each of the data collection activities, including the purpose of the data collection, what will be required of the participant, and any anticipated risks and/or benefits. After each consent statement is read, the participant will be asked whether or not they agree to participate in that data collection activity, and the response will be recorded by the data collector. Participants will be assured that they may decline participation in certain data collection activities, specifically photographic monitoring for a 48 hour period, while still agreeing to participate in all other study activities. All participants will be given contact information for the study personnel. Consent will be sought before pictures of participants are added in reports and publications.

Consent statements, along with surveys and other materials, will be translated into the two local languages (Kasem and Nankam). For some urban households and LPG supply surveys, some participants are likely to opt to take the survey in English. Following NHRC practices, translations are done orally and are developed and agreed upon by interviewers prior to the inception of the surveys. These translations are typically not written down.

XI. PROCESS TO DOCUMENT CONSENT IN WRITING

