- Fire hazard (biomass stoves): Participants will be trained on how to use the stoves properly to avoid fire escaping from the stove and to avoid burns and food losses.
- LPG stove risks: We are taking the following steps to reduce the specific safety risks presented by the LPG stoves being used in this component of the project:
 - EDUCATION: Participants will receive instruction on proper, safe use of LPG at multiple timepoints. Group sensitization meetings will be held in each cluster to present the stove package and explain how to properly use LPG stoves. Project staff will also meet individually with households to make the stove offers, and will address safety concerns during these meetings. Finally, training on proper use will be provided when stoves are

delivered to households, and follow-up visits will be conducted to inspect stoves and ensure that best practices are being followed.

- TECHNOLOGY CHOICE AND DELIVERY MECHANISMS: As noted earlier, the current model of LPG distribution in Ghana involves households purchasing and refilling LPG cylinders. This is thought to lead to potential problems, since households may prefer to use cylinders as long as possible rather than replacing them when they start to wear out. For all households receiving stoves and cylinders in this study, we will instead use a cylinder recirculation model: the refilling station will maintain a stock of filled cylinders (and connecting hoses), and participants will swap empty cylinders for full ones. The refilling station will inspect cylinders for leaks and other issues. This is the international best practice, and Ghana has announced its intention to move toward this model nationwide in the future. Thus, our study participants should face lower LPG-related risks compared to the status quo in this region.
- Risk of jealousy/social discord due to randomization: Steps that will be taken to mitigate this risk include: a) randomizing stove price at the cluster level so that households near one another are charged the same price for their stoves; and b) holding public meetings and following local "community entry" best practices to clearly explain study design at the outset, including making the randomization process transparent as possible to reduce perceptions that the study is "unfair."

Risks associated with data collection:

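### The public P3 Bio price draw comes before household consent and replacement of refusers, and no visible text holds the price back, so enrolment could depend on the drawn price

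*Combined protocol and SAP*

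**What the plan says.** All references are to the combined protocol and SAP.

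- **Draw.** Section VIII, on P3 Bio, says that the team "will randomize the stove discounts transparently during the community entry phase with the participation of representatives from different clusters". Drawing numbers from a hat is only an example, but the timing is stated without qualification. The same section puts community entry in every study cluster ahead of research activities.
- **Consent.** "Following community entry, households that have been randomly selected from each cluster will be visited by the survey interviewers". At that visit the interviewers tell households of their selection and obtain consent.
- **Replacement.** A replacement list is drawn at random together with the initial recruits, and "households that elect not to participate (or are not available / cannot be located) will be replaced with households from this list".
- **Unit.** Section IV (Prices) states that "all households in a cluster will be offered stoves at the same price".
- **Openness.** Section IV says "Randomization of clusters to different price levels will be done in a participatory and transparent manner", and mentions a video of the draw that could be shown to respondents worried about fairness. Section VIII adds that "we will explain our methods as transparently as possible and communicate with leaders and participants at various levels". Section XVII lists public meetings among its measures against discord, "including making the randomization process transparent as possible to reduce perceptions that the study is" unfair.
- **Later steps.** In Section XII, Table 5, consent and the baseline survey are both at Visit 1. P3 Bio stove selection is at Visit 2, and no other survey is scheduled before it.

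**The concern.** Randomising clusters to prices makes the price groups comparable in expectation. That protection reaches the enrolled households only if enrolment does not respond to the price. Here one draw fixes the price for everyone approached in the cluster, and a household that declines is replaced by another facing the same price. If households learn the price first, and those uninterested at that price decline more often, the enrolled sample at positive prices is enriched with buyers and demand looks less price-sensitive. If would-be buyers decline more often, the reverse happens.

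Section IV treats price as exogenous in the regressions for adoption, use and perceived quality, all measured in enrolled households, so each could be affected.

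There is also an unresolved ordering. Research question 1 (Section I) asks how price affects prior perceptions. If the Visit 1 survey is to supply that answer, the price must be known by then, but the plan does not say whether it is disclosed before or after consent.

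**Working it through.** **Order of steps.** From Sections IV, VIII and XII: (1) community entry, including the draw; (2) household visit, consent and baseline survey; (3) replacement of refusers; (4) stove meeting and selection. The price therefore exists before consent. No visible sentence withholds it from households or interviewers until step 3 is complete, and none says that households have been told it by step 2.

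**The plan's own figure.** Table 1 gives power 0.999 for adoption of 100% at P0 (N=70) against 75% at P1 (N=84). I assume a two-sided 5% test and independent households, since Table 1 states neither alpha nor sidedness.
- Pooled proportion: (70 + 63)/154 = 0.864.
- Null SE: √[0.864 × 0.136 × (1/70 + 1/84)] = 0.0555. Alternative SE: √(0.75 × 0.25/84) = 0.0472.
- z = (0.25 − 1.96 × 0.0555)/0.0472 = 2.99, so power is 0.9986. The stated figure reproduces, and this point does not dispute it.

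**Illustration of the bias.** Inputs are the Table 1 adoption assumptions: P0 100%, P1 75%, P2 50% (N=140). I read P0 as the free offer. The documents give no refusal rate, so I assume that a fraction f of 10% to 20% refuses because of price, with none at P0, and that replacements come from the same mix and behave the same way.

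If non-buyers refuse, enrolled adoption = p / [p + (1 − p)(1 − f)]:
- P2: 0.50/0.95 = 0.526 and 0.50/0.90 = 0.556. The P0-P2 effect goes from 50 to 47.4 and 44.4 points.
- P1: 0.75/0.975 = 0.769 and 0.75/0.95 = 0.789. The P0-P1 effect goes from 25 to 23.1 and 21.1 points.
- P1-P2 (75% − 50% = 25 points): 76.9 − 52.6 = 24.3 and 78.9 − 55.6 = 23.4 points (unrounded inputs).
- Refusals implied at P2: 5% to 10% of those first selected, or 7 to 14 of 140.

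If would-be buyers refuse instead, enrolled adoption = p(1 − f) / [p(1 − f) + 1 − p]. At P2 this is 0.45/0.95 = 0.474 and 0.40/0.90 = 0.444, so the P0-P2 effect becomes 52.6 and 55.6 points. If refusal is unrelated to purchase intention, there is no bias.

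**Price-by-peer interaction at P2.** Table 1's 60% and 40% drops from 100% mean 40% adoption in S1 and 60% in S2, a 20-point difference. With non-buyers refusing, S1 becomes 0.426 to 0.455 and S2 becomes 0.625 to 0.652.
- Both groups affected: 19.9 to 19.8 points.
- S1 only: 17.4 to 14.5 points.
- S2 only: 22.5 to 25.2 points.

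The documents give no reason to expect either one-sided case.

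**Detection.** With the P0-P2 effect cut to 44.4 points (100% of 70 against 55.6% of 140), z = (0.444 − 1.96 × 0.0668)/0.0420 = 7.5. With variances doubled (an assumed design effect of 2) it is 4.4. Power exceeds 0.999 either way.

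**Counting refusers as non-adopters.** Suppose 5% to 10% of first-selected households refuse, and the true P0-P2 effect is 50 points.
- Refusal at P2 only, all non-buyers: 50, exact.
- Refusal at P2 only, unrelated to intention: 100 − 50 × 0.95 = 52.5, to 100 − 50 × 0.90 = 55.
- Refusal at P2 only, all would-be buyers: 100 − 45 = 55, to 100 − 40 = 60.
- Unrelated refusal at every price: 95 − 47.5 = 47.5, to 90 − 45 = 45.

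The error reaches 10 points, more than the 5.6-point bias illustrated above.

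**The case against.** The strongest reply is that the decisive step is not in the text. Section VIII lists what participants are told: the two stove prices, that discounts differ by cluster, and that they are set at random. The drawn result is not on that list. The draw involves cluster representatives, not every household. Section X says the consent statement covers the design of the price manipulation, and a rule on disclosure could sit in the removed consent pages. This stands, and it is why the point is conditional.

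The motive to refuse is also weak. Households may take no stove, prices are at or below cost with financing, and participants receive tokens. That stands too, although enrolment carries repeated surveys and, for a subset, monitoring, so an uninterested household could still decline.

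Household selection by nearest-neighbour rules (Section VI) and the pre-drawn replacement list limit interviewer discretion. They do not stop a household from declining because of its price.

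On size, the refusal rates are assumed, and setting P0 adoption at 100% puts all the differential refusal on the positive-price groups. Section IV has some households offered stoves free, while Section XXII describes P3 Bio offers as being at a positive price. The P1-P2 contrast avoids that dependence and moves by only 0.7 to 1.6 points. Even the 2.6 to 5.6-point shift in P0-P2 compares with a standard error of about 4.2 points for adoption at P2 (√(0.25/140), ignoring clustering). This stands as a limit on magnitude. It does not remove the exposure, because more data would not reduce a recruitment bias.

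**Conclusion.** The concern holds in a conditional form. The plan states an order (public draw, consent visit, replacement of refusers) in which enrolment could depend on price, and nothing visible prevents it. Bias arises only if households learn their price before deciding and refusal is related to purchase intention. The documents establish neither condition.

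Under the assumed refusal of 10% to 20% of non-buyers, the P0-P2 effect moves from 50 to 47.4-44.4 points and the P1-P2 effect from 25 to 24.3-23.4. Refusal by would-be buyers moves the P0-P2 effect the other way. No figure can be given for use or perceived quality.

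A reader might infer three stronger things. One is that households are told their price before consent; the text does not say so. Another is that demand will look less price-sensitive than it is; the direction depends on who refuses. The third is that the study may miss the price effect; the large P0-P2 effect would still be detected. What is exposed is the size of the estimates. The change is cheap enough to be worth making.

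**What to change.** Keep the transparent draw, but hold it, or reveal its result to households and interviewers, only after consent and all replacements are complete in the 50 P3 Bio clusters and before Visit 2. Allow no replacements afterwards. Ask the prior-perception items for research question 1 at the already scheduled Visit 2, after the price is announced and before stoves are chosen.

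The cost is a later draw, possibly one more gathering of representatives, and a few added items at Visit 2. Those items should be brief, since questions asked just before selection could influence the choice.

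This version is dated 11 January 2018, in Year 3 of the workplan, so the draw may already have taken place. In that case, tabulate recorded refusals and replacements by price level and S1/S2, and compare baseline characteristics by price. Section X says of each consent question that the participant is asked for agreement "and the response will be recorded by the data collector". It does not establish that households declining earlier, or never located, were logged, so any gap should be reported. An analysis counting refusers as non-adopters should be shown only as one bound, because it is exact only if every refuser is a non-buyer. The cost is then one table and a balance check.

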S1 group households will be selected using GIS data to identify the *nearest neighbors*, meeting the above eligibility criteria, of each of the 6 REACCTING households that received stoves in that cluster during the REACCTING intervention phase. In the non-peer clusters, 6 seed households meeting the above eligibility criteria will be randomly selected, and then S2 group households will be selected as the nearest neighbors of those seed households. This procedure is used to create as similar as possible selection criteria and sampling methods between the peer (S1) and non-peer (S2) groups.

Component #2: P3 Gas

This component of the study involves two subject populations: LPG suppliers, and urban households. For the supply survey, all LPG refilling stations in the Upper East Region, and all retail shops selling LPG stoves or cylinders in the K-N Districts, will be eligible for inclusion in the study (16 businesses in total).

For the urban households, we will use the same demographic inclusion criterion as in the rural sample (at least one woman in household aged 18-55 and one child under five). As in the rural areas, we will first randomly select clusters from the urban area, and then randomly select households within each cluster, for a total of 300 households in this component. These subjects will complete an initial baseline survey (Activity 1.2) and will then be enrolled in the intervention (Activity 2.1) and follow up data collection. In the urban area, the majority of respondents belong to the Kasem ethnic group. As above, the primary cook is the primary participant, and if another individual in the household is responsible for making financial decisions for the household, this individual will also complete household surveys and will be present when stove offers are made.

VII. VULNERABLE POPULATIONS

> Not applicable.

VIII. RECRUITMENT METHODS

P3 Bio and P3 Gas Household Recruitment

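### Section VIII's random recruitment and replacement wording conflicts with Section VI's nearest-neighbour rule for P3 Bio, and random replacement in S1 could weaken the S1–S2 peer contrast

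*Combined protocol and SAP*

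**What the plan says.** Section VI (Inclusion / Exclusion Criteria) builds a frame of eligible rural households. In a further step it uses GIS data to choose S1 households as the nearest eligible neighbours "of each of the 6 REACCTING households that received stoves in that cluster during the REACCTING intervention phase". For the comparison clusters, six eligible seeds are drawn at random, and "S2 group households will be selected as the nearest neighbors of those seed households". The reason given is: "This procedure is used to create as similar as possible selection criteria and sampling methods between the peer (S1) and non-peer (S2) groups".

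Section VIII (P3 Bio and P3 Gas Household Recruitment) opens differently: "Study households will be randomly selected from the sample frame of eligible households constructed using the methods described in Part VI". After community entry, "households that have been randomly selected from each cluster will be visited by the survey interviewers". On non-participation it says "A list of replacement households from each cluster will be randomly draw along with the initial recruits", and then "households that elect not to participate (or are not available / cannot be located) will be replaced with households from this list". No distance or seed condition is attached to that list.

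I found no expected replacement rate, no flag for replaced households and no analysis that sets them apart.

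**The concern.** The S1–S2 comparison is the study's test of peer effects. Section IV (Peer Effects) rests S1's exposure on physical closeness to REACCTING households and the social ties expected to follow. Choosing nearest neighbours of actual stove recipients pushes that exposure up. A replacement drawn from anywhere in the cluster carries no such guarantee: Section III says a cluster can contain up to 99 compounds.

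If exposure declines with distance from a recipient, random replacement lowers mean exposure in S1. It does not change exposure to stove owners in S2. The contrast would then move toward zero, with a loss of power on a main comparison in Table 1. Field staff would follow Section VIII when a household refuses or cannot be found, so the wording matters in practice.

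**Working it through.** **Does the reference back to Part VI settle it?** The opening sentence of Section VIII refers to Part VI for how the *sample frame* was built. In Section VI the frame is the list of households meeting the eligibility criteria (rural, biofuel as main fuel, a woman aged 18–55, a child under five). Nearest-neighbour selection is a later step applied to that list. Read as written, Section VIII draws at random from the frame, for initial recruits and replacements alike. Random selection within clusters agrees with Section VI for P3 Gas and disagrees with it for P3 Bio.

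**How thin is the proximity sample?** Table 3 gives 150 S1 households, and Section VI gives 25 S1 clusters: 150 / 25 = 6 per cluster, or about one neighbour for each of the six stove recipients.

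**Reproducing Table 1.** Inputs for the peer effect on adoption: 75% in S2, 60% in S1, n = 147 per group, stated power 0.838. Alpha and sidedness are not stated. The figure reproduces with a one-sided 0.05 test, pooled null variance, a continuity correction of 1/n and no allowance for clustering:

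- SE under the null = √(2 × 0.675 × 0.325 / 147) = 0.0546
- SE under the alternative = √((0.75 × 0.25 + 0.60 × 0.40) / 147) = 0.0539
- Power = Φ[(0.15 − 1/147 − 1.645 × 0.0546) / 0.0539] = Φ(0.989) = 0.839

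The same method gives 0.714 for the interaction row (stated 0.7112). Without the continuity correction the adoption figure is 0.868 one-sided or 0.787 two-sided, so neither of those is the plan's baseline.

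**Dilution.** Let r be the share of S1 replaced and k the share of the peer effect that a replacement keeps. Neither is in the documents; both are assumed. The difference becomes 15 × [1 − r(1 − k)] points. For example:

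- r = 10%, k = 0.5: 15 × (1 − 0.10 × 0.5) = 14.25 points
- r = 20%, k = 0: 15 × (1 − 0.20) = 12 points

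Difference in points and power, holding S2 at 75%:

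| r | k = 0 | k = 0.5 | k = 0.75 | k = 1 |
|---|---|---|---|---|
| 5% | 14.25; 0.804 | 14.6; 0.822 | 14.8; 0.830 | 15; 0.839 |
| 10% | 13.5; 0.765 | 14.25; 0.804 | 14.6; 0.822 | 15; 0.839 |
| 20% | 12.0; 0.676 | 13.5; 0.765 | 14.25; 0.804 | 15; 0.839 |
| 30% | 10.5; 0.575 | 12.75; 0.723 | 13.9; 0.785 | 15; 0.839 |

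Power drops below 0.80 at r of about 5.6% (k = 0), 11.2% (k = 0.5) or 22.3% (k = 0.75).

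**Perceived quality.** Table 1 assumes 10 points, SD 25, 147 per group and power 0.96. A one-sided 0.05 normal test gives Φ[10 / (25√(2/147)) − 1.645] = 0.963. At r = 10%, k = 0.5 this becomes 9.5 points and 0.947; at r = 20%, k = 0, 8 points and 0.864.

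**The case against.** The strongest reply is that Section VIII is loose wording shared by two components. Random selection is the true method for P3 Gas, the replacement list is drawn together with the initial recruits, and a sympathetic reader could take both to follow Part VI. That is possible, but the text does not say so, and its cross-reference reaches only the frame. It also means that the conflict covers the initial recruits, not just the replacements.

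The second reply concerns harm. A reader might infer that every S1 replacement dilutes exposure. The documents do not support that:

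- Section IV defines S1 by being in the same clusters as the REACCTING households, and one planned exposure variable is prior adoption and usage at cluster level. A same-cluster replacement keeps both.
- A random draw can land close to a recipient. Ninety-nine compounds is a maximum. About 30,000 households (Section III) over more than 300 clusters (Section IV) averages fewer than 100 households per cluster, before eligibility is applied. Each S1 cluster has six stove recipients, and two control households are due a stove at about the time this project starts.
- k = 0 gives a household in a REACCTING cluster no more peer effect than one in S2, so it is an extreme bound.

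A reader might also infer that the match in sampling between S1 and S2 is lost. It is not: the same replacement rule applies in both groups. The match is weakened, because some households in each group would no longer be chosen by proximity, and it would become unbalanced only if replacement rates differed. The documents give no sign that they would.

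Finally, the study already collects compound coordinates (Table 6) and social-network data (Table 4), so exposure can be partly checked afterwards. That stands, but it does not tell field staff whom to approach next.

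**Conclusion.** The conflict between Sections VI and VIII is real and unresolved for P3 Bio. Attenuation of the peer effect is a conditional risk: it requires that replacements are actually drawn at random and that exposure falls with distance inside a cluster.

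Under those conditions the loss is r(1 − k) of the effect. Plausible inputs range from nothing (k = 1), through a modest loss (14.25 points, power 0.80), to a material one at the extreme (12 points, power 0.68). It would go too far to say that the plan *will* understate the peer effect, or by how much, because the documents give neither r nor k. All the power figures use the one-sided, unclustered calculation that reproduces Table 1. They show the change caused by dilution and do not endorse that calculation.

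The point deserves correction because it touches a main contrast and costs almost nothing to settle.

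**What to change.** For P3 Bio only, leaving P3 Gas as it is:

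1. In Section VIII, state that initial recruits are chosen by the nearest-neighbour rule of Section VI, and confine the random-selection wording to P3 Gas.
2. State that a household that cannot be enrolled is replaced by the next-nearest eligible neighbour of the same REACCTING household (S1) or the same seed household (S2).
3. Record replacement status and the reason, and report replacement rates by group.
4. Compute each household's distance to its REACCTING or seed household from the coordinates already collected.
5. Pre-specify a sensitivity analysis of the S1–S2 comparison that excludes replacements. It removes the dilution, but not any selection due to refusal, and it has fewer households.

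The cost is a few sentences, one extra recorded field and one extra analysis. The GIS data are already part of the plan, and no households or visits are added. If recruitment has already been done, steps 3 to 5 can still be carried out wherever field records show who was replaced, and the report should state which rule was used.
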